## Section 5.6 Dose Justification

A loading dose of GSK3036656 may be administered on the first day of study treatment administration in each cohort. The long half-life of GSK3036656 (45 hours) means that subjects will take up to 10 days to reach steady-state concentrations, which is not optimal for a 14-day treatment study. A loading dose will allow participants to reach steady-state concentrations in 2 to 3 days for a given maintenance dose regimen.

The probability rates for individual participants to exceed GSK3036656 exposure limits and achieve the efficacy target for proposed loading and maintenance dose regimens are shown in Table 1.

**Table 1 Probability rates of individual participants for proposed loading and maintenance doses**

Loading Dose (mg) a	Probability Day 1 c	Maintenance Dose (mg) b	Probability Day 14 d	Target Attainment Rate e
10	< 1%	2.5	< 1%	< 1%
15	< 1%	5	< 1%	< 1%
20	2.4%	10	7.9%	100%

a Day 1

b Day 2-14

c per trial probability of an individual participant exceeding the exposure limits [AUC0-24 = 4.9 ug.h/mL or Cmax = 0.443 ug/mL] on Day 1 (simulations based on a lower limit of 75 mL/min for creatinine clearance)

d per trial probability of an individual participant exceeding the exposure limits [AUC0-24 = 4.9 ug.h/mL or Cmax = 0.443 ug/mL] on Day 14 (simulations based on a lower limit of 75 mL/min for creatinine clearance)

e per trial probability of >90% of participants exceeding the target exposure for efficacy

The starting dose regimen for this study will be 15 mg loading dose on Day 1 and 5 mg maintenance dose on Day 2-14, based on the above information, with the option to investigate a lower dose in subsequent cohorts should the preliminary data indicate this is appropriate.

**The loading dose (if applicable) and maintenance dose for each cohort will be chosen on the basis that it is not predicted to exceed the pre-specified safety cap, and the dose used will be decided by the Dose Escalation Committee (Section 11).**

#### Section 6.1. Inclusion Criteria

**8. A creatinine clearance  $\geq 75$  mL/min (Cockcroft-Gault formula).**

#### Section 6.2 Exclusion Criteria

~~3. A previous episode of treated TB less than 3 years ago.~~

#### Section 8.1.3 8.1.3. Haematology Stopping Criteria

- **A reduction in neutrophil count to below  $500/\text{mm}^3$  ( $0.5 \times 10^9/\text{L}$ ).**

#### Section 9.3 Treatment of Overdose

For this study, any total dose of GSK3036656 greater than the dose selected for that cohort (**taken within a 23-hour period**) will be considered an overdose.

#### Section 10.3.4 Efficacy Analyses

No formal interim analyses are planned for this study. However, safety, tolerability and pharmacokinetic data will be reviewed before each dose escalation. **In addition, the primary efficacy endpoint may also be analysed after the final visit of the last subject for the cohort which receives the anticipated highest dose.** See Section 11 for further details.

#### Section 11 Dose Escalation

After the initial dose of GSK3036656, the decision to proceed to each subsequent dose level will be made by the Dose Escalation Committee (DEC) based on safety, tolerability and preliminary GSK3036656 pharmacokinetic data from the prior cohort. **The DEC may also include in their deliberations, efficacy data, if that is available.** Minimum requirements for data are as follows: PK data in at least 10 subjects receiving GSK3036656 and selected safety data from all subjects in a cohort. A dose escalation committee charter will be produced that will contain the following details:

- Committee members
- Data review requirements
- Process for informing the ethics committee of any safety concerns if appropriate
- Facility for requesting additional pertinent information from the investigator

Dose escalation will be based on population PK modelling (if feasible). ~~or on the assumption of dose-exposure proportionality (i.e., doubling the dose gives an approximate doubling of exposure).~~ If prior PK results show less than proportional

~~increase in exposure with increasing dose, the prediction will be based on the assumption that the fold exposure increase to fold dose increase ratio will be the same with the current dose escalation as it was with the previous one. If prior PK results show more than proportional increase in exposure with dose, subsequent.~~ **Dose escalations will not be higher than 3-fold.**

The population PK model will be a fit for purpose model. Candidate model selection will be primarily based on a significant reduction in the objective function value ( $\geq 3.32$ ,  $\chi^2 < 0.05$ ) and improvement in the fits of diagnostic scatter plots. Inter-individual variability will be modelled using an exponential error model and residual error will be described by a proportional, proportional plus additive, or additive error model, depending on the data. Model performance will be evaluated using a visual predictive check. Simulations for dose recommendations will be conducted to determine the probability of an individual subject exceeding the defined exposure margins for AUC and Cmax.

**Alternatively, if a population PK model is not feasible, dose escalation will be based on a dose-exposure model of the form:**

$$\log(\text{AUC}) = a + b \cdot \log(\text{DOSE}) + c \cdot \log(\text{BWT}/70)$$

$$\log(\text{C}_{\text{MAX}}) = d + e \cdot \log(\text{DOSE}) + f \cdot \log(\text{BWT}/70)$$

**where a and d are AUC and Cmax values, respectively; c = -0.75 and f = -1.00 are set values for allometric scaling; and b and e are scaling factors for dose proportionality.**

A proposed dose will be acceptable if the predicted probability of an individual exceeding pre-defined exposure limits (Section 5.6) on any day of the dosing period, as estimated by PK modeling, is no more than 10%.

**The primary endpoint may be analysed for all available cohorts after the final visit of the last subject for the cohort which receives the anticipated highest dose (as determined by the DEC). The purpose of this efficacy analysis is to optimise dosing for subsequent cohorts (e.g. to help estimate the dose response curve) as well as to aid internal decision making.**

**The DEC is empowered to take the following decisions for subsequent cohorts:**

- **To select a higher dose within the limits defined in section 5.6.**
- **To select a dose lower than, or the same as, a preceding dose.**
- **To stop dosing.**
- **To include additional pharmacokinetic assessments.**
- **To include additional timepoints for existing safety assessment.**

## Section 13.6 Appendix 6

## Contraception Guidance

## Male participants

- Male participants with female partners of child-bearing potential are eligible to participate if they agree to ONE of the following:
  - Are abstinent from penile-vaginal intercourse as their usual and preferred lifestyle (abstinent on a long term and persistent basis) and agree to remain abstinent **for a period of 90 days after the last dose of study medication (one spermatogenesis cycle)**.
  - Agree to use a male condom plus an additional method of contraception with a failure rate of <1% per year as described in Table 3 when having penile-vaginal intercourse with a woman of childbearing potential.
- Men with a pregnant or breastfeeding partner must agree to remain abstinent from penile-vaginal intercourse or use a male condom during each episode of penile penetration during the treatment period and for **6 days after (five terminal half-lives)**.
- In addition, male participants must refrain from donating sperm during the treatment period and for **90 days after (one spermatogenesis cycle)**.

**Amendment 1 (20-Feb-2018)**

**Overall Rationale for the Amendment:**

[figure not shown]
CCI [REDACTED]

CCI [REDACTED] Minor typographical corrections throughout the document have also been applied.

Section #	Description of Change	Brief Rationale
3.3.1	
CCI [Redacted]
 
3. Correction of typographical error regarding menstruation
	Clarity and consistency of the document and implementation of additional safety measures for participants
5.1	CCI [Redacted]	Design clarity
6.1 & 6.2	
1. CCI [Redacted] must be 25 years of age or older.
 
2. Wording clarification for inclusion criteria #5
 
3. Wording clarification for inclusion criteria #6
 
4. Wording clarification for exclusion criteria #11
 
CCI [Redacted]
 
6. Changed text to match 3.3.1 regarding menstruation
	Design clarity & clarity and consistency of the document.
9.1	Clarification wording in section header and definition of timepoint nomenclature	Clarity and consistency of the document
9.6& 13.8	CCI [Redacted]	
All document	Minor typographical corrections	Clarity of document

**Section 3.3.1 Risk Assessment**

CHANGES

	
-The level of risk may therefore be assumed to broadly fall within the ICRP 62 intermediate Category IIb, where the benefit should be more directly aimed at the cure or prevention of disease.
	
CCI [REDACTED]
 
CCI [REDACTED] Clinically justified (therapeutic or diagnostic) exposures are not included in the exposure calculation. Participants are asked about any occupational exposure or previous participation in research studies at screening so that dose estimates can be obtained where necessary.
 
The study will exclude women of childbearing potential.
 
CCI [REDACTED]

--	--	---

		CCI
--	--	-----

### Section 5.1 Overall Design

#### CHANGES

**In addition, the minimum age for inclusion for participants recruited to these 2 cohorts will be raised from  $\geq 18$  to  $\geq 25$  years old.**

### Section 6.1 Inclusion criteria

#### CHANGES

#### Age

1. Participant must be 18 to 65 years of age inclusive, at the time of signing the informed consent.
2. CCI

### Section 9.1 Microbiological Efficacy/Activity Assessments

#### CHANGES

**Drug activity with CFU or TTP over different treatment periods such as baseline - Day2, and Day2-14, for cross-comparison with other published data. Data will be displayed graphically, together with modelled estimates.**

[figure not shown]
**For the purposes of the microbiological endpoints assessments, the pre-treatment baseline will be defined as either Day -2 and/or Day -1.**

**Mycobacterial Characterisation:**

The identifying organism will be confirmed as *Mycobacterium tuberculosis* at least once by polymerase chain reaction (PCR) at screening (GeneXpert or Line Probe) and a sample collected before treatment will be submitted for culture confirmation.

**Section 9.6. Potential Surrogate Disease/Biomarkers****CHANGES**

CCI

CCI

**Description:**

- The purpose of this RAP is to describe the planned analyses and output to be included in the Clinical Study Report (CSR) for Protocol TMF-13331420.
- This RAP is intended to describe analysis requirements during the study to support the dose escalation analyses and the final analyses required for the study in terms of conveying the content of the Statistical Analysis Complete (SAC) deliverable.

## 1. INTRODUCTION

The purpose of this reporting and analysis plan (RAP) is to describe the analyses to be included in the Clinical Study Report for Protocol:

Protocol Revision Chronology:		
2017N332005_00	09-FEB-2018	Original
2017N332005_01	20-FEB-2018	Protocol Amendment 1: CCI 
2017N332005_02	24-SEP-2018	Protocol Amendment 2: The primary motivation for this amendment was to update the eligibility criteria to impose a minimum renal function (as defined by creatinine clearance) in light of the first-in-human data that showed the main route of clearance for GSK3036656 is through the kidneys. As a result of the long half-life of GSK3036656, an updated dosing strategy has also been implemented incorporating the use of loading doses.
2017N332005_03	24-JUL-2019	Protocol Amendment 3: To document the increase in exposure limits and change in eligibility criteria following the availability of new non-clinical data.
TMF-11820616	17-FEB-2021	Protocol Amendment 4: To allow for standard of care medication administered in the study to be either Rifafour e-275 or an equivalent generic alternative and to allow for analysis of the primary endpoint data to be performed on additional cohorts.
TMF-13331420	12-MAY-2021	Protocol Amendment 5: Variability in the rate of change of log 10 CFU observed in the trial to-date is lower than anticipated. Due to this, and slower than anticipated recruitment, the study sample size has been re-calculated. The potential to modify the haemoglobin exclusion and stopping criteria in subsequent cohorts investigating lower doses of GSK3036656 has been added.

## 1.1. RAP Amendments

RAP Version	Approval Date	Protocol Version (Date) on Which RAP is Based	Change	Rationale
Reporting and Analysis Plan 201214 Final V1	11-DEC-2018	Protocol Amendment 2 (24-SEP-2018)	N/A	Original Version
Reporting and Analysis Plan 201214 Amendment1 V0.1	Refer to document date	Protocol Amendment 5 (12-MAY-2021)	
 
1. Section 2.3: Study Design – The number of participants per treatment arm has been changed from 20 to 12-20.
 
2. Section 7.1.5.1: Statistical Methodology Specification – For the analysis of the primary endpoint a mixed model with repeated measures analysis has been added as the primary analysis. Dose has been replaced by treatment, with data for participants receiving standard-of-care included, and BMI has been added as a covariate.
 
3. Section 10: Additional Analyses Due to the COVID-19 Pandemic – Additional study population and safety displays have been added.
 
4. Section 12.4.1.2: Phases of COVID-19 Pandemic measures – details have been added as to how to
 
	
 
1. The required number of participants for the later cohorts was reduced in protocol amendment 5.
 
2. A repeated measures analysis, including day as a covariate is more appropriate for measuring the rate of change over the entire 14 day treatment period. It is important to understand the effect of SoC on the endpoint. BMI has a potential influence on the EBA endpoints.
 
3. In order to understand the impact of the COVID-19 pandemic on the study conduct and the results, additional summaries are required.
 
4. The COVID-19 pandemic began at different times in
 

			
determine when the pandemic began for the categorisation of AEs.
 
5. Minor clarifications and corrections.
	
different countries with multiple waves. Guidance is therefore required for determining timings.
 
5. Minor clarifications and corrections have been made where wording was ambiguous/vague or errors were identified to improve the accuracy and comprehensiveness of the RAP.

--	--	--	---	---

## 2. SUMMARY OF KEY PROTOCOL INFORMATION

### 2.1. Changes to the Protocol Defined Statistical Analysis Plan

The change or deviation to the originally planned statistical analysis specified in the protocol amendment 5 [(Dated: 12/MAY/2021)] is mentioned below.

Protocol	RAP	Rational
Section 10.3.1: Activity/ Pharmacokinetic Analyses	Section 7.1.5.1: Model 2: Bi-linear Bayesian regression model	The model 2 Bi-linear regression analysis has been added as an additional supportive analysis. This is recommended for the analysis of EBA endpoints in TB due to them sometimes following a bi-linear rate of change.

### 2.2. Study Objective(s) and Endpoint(s)

Objectives	Endpoints
Primary Objectives	Primary Endpoints

 
To determine the early bactericidal activity of GSK3036656 over 14 days of once daily repeat dosing.
 
	
 
Rate of change in log10CFU per ml direct respiratory sputum samples over the period baseline to Day 14 (EBA CFU0-14).
 

Secondary Objectives	Secondary Endpoints

 
To assess the safety & tolerability of GSK3036656 administered once daily over 14 days to patients with tuberculosis.
 
	
 
Adverse events (AE), clinical laboratory values, vital signs, electrocardiogram (ECG) parameters.
 

 
To characterise the pharmacokinetics of 14-day once daily dosing of GSK3036656 in tuberculosis patients
 
	
 
Derived pharmacokinetic parameters for GSK3036656 including area under the plasma drug concentration versus time curve (AUC(0-t), AUC (0-24)), maximum observed plasma drug concentration (Cmax), and time to maximum observed plasma drug concentration (tmax), as appropriate.
 

 
To determine the early bactericidal activity of GSK3036656 over the first 2 days and the last 12 days with 14 days of once daily repeat dosing.
 
	
 
Rate of change in log10CFU per ml direct respiratory sputum samples over the period baseline to Day 2 (EBA CFU0-2).
 
Rate of change in log10CFU per ml direct respiratory sputum samples over the period Day 2 to Day 14 (EBA CFU2-14).
 
Rate of change in time to sputum culture
 

Objectives	Endpoints
	positivity (TTP) over the time period baseline to Day 14 (EBA TTP 0-14 ) 
 
• Rate of change in time to sputum culture positivity over the time period baseline to Day 2 (EBA TTP0-2)
 
• Rate of change in time to sputum culture positivity over the time period Day 2 to Day 14 (EBA TTP2-14)
 

Exploratory Objectives	Exploratory Endpoints
CCI	

For the purpose of assessment of bacterial CCI endpoints, the pre-treatment baseline will be defined as the mean of Day -2 and Day -1; if data is available at only Day -2 or Day -1 then that value will be used as baseline. For ECG endpoints, baseline is screening. CCI

### 2.3. Study Design

Overview of Study Design and Key Features	
<pre> graph LR     A[SCREENING from -9 days prior to first dose] --> B[14-Day treatment period - GSK3036656]     A --> C[14-Day treatment period - Rifafour]     B --> D[Day 15 start/continue Rifafour*]     C --> D     D --> E[Follow-up at Day 28]             </pre> 
*This is not part of the study but is the post-study definitive treatment of TB.
	
Design Features	
 
• A single-centre, open-label trial in up to five sequential cohorts.
 
• Each cohort will involve participants being randomised to one of two possible treatments: either GSK3036656 or Standard-of-Care (SoC) regimen (e.g. Rifafour®e-275) for rifampicin-susceptible (drug sensitive) tuberculosis (DS-TB).
 
• Screening will be performed on days -9 to -1, followed by 14 days of once daily dosing and a follow-up visit 28 days after the first dose.
 
• All laboratory staff involved in analysing and reporting the primary and secondary change in CFU counts and TTP endpoint results will be blinded to treatment allocation.
 

Dosing	
 
• Once daily repeat dosing for 14 days.
 
• The starting dose for the GSK3036656 arm is a 15mg loading dose on Day 1 and 5mg maintenance dose on Days 2-14, given orally. The study will employ dose escalation, where the GSK3036656 dose for each cohort will be decided based on reviews of preliminary safety, tolerability and pharmacokinetic data; in addition, efficacy data will be considered if available.
 

Time & Events	
 
• See Appendix 2: Schedule of Activities
 

Treatment Assignment	
 
• 12-20 participants in each cohort (excluding possible replacements), randomised 3:1 to GSK3036656 or Standard of Care respectively.
 
• GSK RandAll NG will be used to generate the randomisation schedule.
 

Dose Escalation Analysis	
 
• No formal interim analysis is planned.
 
• Safety, tolerability and pharmacokinetic data will be reviewed before each dose escalation.
 
• The primary endpoint may be analysed (including data from all available cohorts) as part of the dose escalation analyses. The earliest this can occur is after the final visit of the last subject on the second consecutive cohort that reaches or exceeds the target PK plasma exposure for efficacy..
 

## 2.4. Statistical Analyses

The primary endpoint, EBA CFU0-14, will be analysed using a mixed effects model including treatment, day, BMI and treatment-by-day as covariates. Secondary endpoints of EBA CFU0-2, CFU2-14, TTP0-2, TTP0-14 and TTP2-14 will be analysed similarly to the primary endpoint. See Section 7: Efficacy Analyses for further details.

Plasma concentration-time data will be analysed by non-compartmental methods, the following pharmacokinetic parameters will be determined: Maximum observed plasma drug concentration (Cmax), Time to maximum observed plasma drug concentration (tmax), Area under the concentration-time curve from time of dosing to last quantified concentration, regardless of time (AUC(0-t)), Area under the concentration-time curve from time of dosing extrapolated to 24 hours (AUC(0-24)) and Trough Concentration (Cτ). AUC(0-t) or AUC(0-24) and Cmax may be used for assessment of dose proportionality. Trough concentration (Cτ) samples will be used to assess attainment of steady state. See Section 9 for further details.

Safety data, including AEs, clinical laboratory values, vital signs and ECG, will be summarised descriptively according to GSK's Integrated Data Standards Library (IDSL) standards. See Section 8: Safety Analyses for further details.

### 3. PLANNED ANALYSES

#### 3.1. Interim Analyses

No formal interim analyses are planned for this study. However, safety, tolerability and pharmacokinetic data will be reviewed before each dose escalation. In addition, the primary endpoint may be analysed, including data from all available cohorts, after the final visit of the last subject on the second consecutive cohort that reaches or exceeds the target PK plasma exposure for efficacy.

#### Dose Escalation

#### Pharmacokinetic (PK) Analysis

Dose escalation will primarily be based on population PK modelling.

The population PK model will be a fit for purpose model. Candidate model selection will be primarily based on a significant reduction in the objective function value ( $\geq 3.32$ ,  $\chi^2 < 0.05$ ) and improvement in the fits of diagnostic scatter plots. Inter-individual variability will be modelled using an exponential error model and residual error will be described by a proportional, proportional plus additive, or additive error model, depending on the data. Model performance will be evaluated using a visual predictive check. Simulations for dose recommendations will be conducted to determine the probability of an individual participant exceeding the defined exposure margins for  $AUC_{0-24}$  (4.9  $\mu\text{g}\cdot\text{h}/\text{mL}$ ) and  $C_{\text{max}}$  (0.443  $\mu\text{g}/\text{mL}$ ).

Alternatively, if a population PK model is not feasible, dose escalation will be based on a dose-exposure model of the form:

$$\log(\text{AUC}) = a + b \cdot \log(\text{DOSE}) + c \cdot \log(\text{BWT}/70)$$

$$\log(\text{C}_{\text{MAX}}) = d + e \cdot \log(\text{DOSE}) + f \cdot \log(\text{BWT}/70)$$

where a and d are AUC and  $C_{\text{max}}$  values, respectively; c = -0.75 and f = -1.00 are set values for allometric scaling; and b and e are scaling factors for dose proportionality.

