## 5.6. Dose Justification

A population pharmacokinetic model was developed based on preliminary concentration-time data obtained in the FTIH study. The model was used to simulate loading and maintenance doses for GSK3036656 based on the EBA study design and accounting for

the effect of renal impairment on exposure (preliminary data suggest GSK303656 is > 70% renally excreted). A target exposure for efficacy of 1.74 ug.h/mL was set based on the exposure associated with efficacy in a mouse infection model and the target attainment rate was defined as the percentage of participants with an AUC0-24 greater than this target exposure. Exposure limits of AUC0-24 of 15 ug.h/mL and Cmax of 1.5 ug/mL were set, based on information in Section 3.3.

A loading dose of GSK3036656 may be administered on the first day (or over multiple days where required in order to not exceed AUC and Cmax exposure limits) of study treatment administration in each cohort. The long half-life of GSK3036656 (45 hours) means that subjects will take up to 10 days to reach steady-state concentrations, which is not optimal for a 14-day treatment study. A loading dose will allow participants to reach steady-state concentrations in 2 to 3 days for a given maintenance dose regimen.

The probability rates for individual participants to exceed GSK3036656 exposure limits and achieve the efficacy target for proposed loading and maintenance dose regimens are shown in Table 1.

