**Table 1 Probability rates of individual participants for proposed loading and maintenance doses**

Loading Dose (mg) a	Probability Day 1 c	Maintenance Dose (mg) b	probability Day 14 d	Target Attainment Rate e
15	<1%	5	<1%	<1%
25	<1%	10	<1%	100%
50	<1%	20	<1%	100%
75	6.90%	30	5.80%	100%
a Day 1				
b Day 2-14				
c per trial probability of an individual participant exceeding the exposure limits [AUC 0-24 = 15 ug.h/mL or C max = 1.5 ug/mL] on Day 1 (simulations based on a lower limit of 75 mL/min for creatinine clearance)				
d per trial probability of an individual participant exceeding the exposure limits [AUC 0-24 = 15 ug.h/mL or C max = 1.5 ug/mL] on Day 14 (simulations based on a lower limit of 75 mL/min for creatinine clearance)				
e per trial probability of >90% of participants exceeding the target exposure for efficacy				

The starting dose regimen for this study will be 15 mg loading dose on Day 1 and 5 mg maintenance dose on Day 2-14, based on the above information, with the option to

investigate a lower dose in subsequent cohorts should the preliminary data indicate this is appropriate.

The loading dose (if applicable) and maintenance dose for each cohort will be chosen on the basis that it is not predicted to exceed the pre-specified safety cap, and the dose used will be decided by the Dose Escalation Committee (Section 11).

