**Amendment 3 24-JUL-2019****Overall Rationale for the Amendment:**

To document the increase in exposure limits and change in eligibility criteria following the availability of new non-clinical data.

Further changes made to the protocol are detailed in the table below.

Section #	Description of Change	Brief Rationale
Schedule of Assessments table	CCI	Duplication of tests unnecessary.
Schedule of Assessments table; footnote E	Removal of "oral" from footnote	Site primarily use tympanic or axillary temperature assessment.
Schedule of Assessments table; footnote F	Minor re-wording.	Clarity of understanding.
Schedule of Assessments table; footnote H	Remove footnote reference to Day 15	Not required, discrepancy in the protocol found by Investigator.
Schedule of Assessments table; footnote K	CCI	Minimisation of risk to participants.
Schedule of Assessments table; footnote O	Added text that MIC samples sent to GSK, Spain will not be reported in CSR.	To clarify that the MIC testing of the bacterial isolates sent for further characterization to GSK Spain will be reported and analysed separately.
SoA	Addition of an ECG at the Early Withdrawal Visit (EWW)	Mistakenly omitted in previous versions
SoA PK table	
Addition of 10-minute window for the pre-dose ('0') timepoint on Day 14.
 
Clarification that timing of PK samples from Day 14 is relative to dosing on Day 14
 
Addition of PK sample window allowances table
	
Window necessary to ensure all assessments and procedures can be completed in a timely manner.
 
Ensure clarity of understanding.

Section #	Description of Change	Brief Rationale
9.6.1	CCI	
Appendix 3	
Removal of text "The results of each test must be entered into the CRF"
 
Removal of 'urine alcohol'
 
Removal of urine hCG, FSH and oestradiol in females
	
Data will be transferred electronically
 
Urine alcohol test erroneously listed in Appendix 3 but not in table of events. This test will not be done. This is standard GSK template text that should not have been part of this protocol.
 
Females will be excluded

3.3	New AUC & Cmax exposure limits and supporting non-clinical information	New non-clinical data supports increasing the AUC & Cmax limits dictating dose level choices in the study

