5.1	Increase in maximum number of cohorts	To provide flexibility for 3 potential scenarios: a lower dose is included to help describing the exposure-response relationship, a dose needs to be repeated or a higher dose than currently projected is feasible due to observed PK being overpredicted.
5.6	Updated probability rates table based on increased AUC & Cmax exposure limits	New non-clinical data supports increasing the AUC & Cmax limits dictating dose level choices in the study
6.1	Removal of eligibility of females Other criteria re-wording	New non-clinical data indicates females must not be enrolled.
6.2	Addition of 'Female' to exclusion criteria Other criteria re-wording	New non-clinical data indicates females must not be enrolled.
6.3.1	Removal of UV exposure restriction	New information from non-clinical studies now supports removal of the restriction.

Section #	Description of Change	Brief Rationale
6.3.2	Removal of a requirement to abstain from water for a period of time after dosing	Study treatment can be administered without regard to food/water.
8	Addition of text clarifying discontinuation of study treatment	A subject can be discontinued from receiving study treatment but remain in the study.
9.1	Clarification of technical details for MIC provided in other documentation	Per standard practice, technical details are included in a different study document.
9.2.6	Updated text to reflect exclusion of females	New non-clinical data indicates females must not be enrolled.
9.4.1	Removal of the description of a brief physical exam	Not required in this protocol and was template text that should have been removed originally.
9.6.1	CCI	Text required for internal GSK purposes
9.6.2	Replacing text to clarify genetic testing. Addition of text clarifying process for analysis	Human DNA testing will not be conducted. Text required for internal GSK purposes
10.1	Updated number of subjects	Consistency with updated design intent.
10.3.1	Updated clarification of reporting of exploratory endpoints	Clarity of understanding of intent.
10.3.4	Updated text concerning data review triggers	Clarity of understanding of intent.
11	Updated text concerning data review triggers	Clarity of understanding of intent.
Appendix 3	Updated screening tests	Consistency with design intent.
Appendix 4	Addition of text clarifying entities that may receive data	Consistency with design intent.

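### SAP Section 3.1 still prints the superseded Amendment 2 exposure limits (4.9 and 0.443) for the dose simulations; the current protocol sets 15 and 1.5

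*SAP*

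**What the plan says.** SAP Section 3.1, under Dose Escalation, says the population PK simulations estimate the probability of an individual "participant exceeding the defined exposure margins for $AUC_{0-24}$ (4.9" ug.h/mL). The same sentence gives 0.443 ug/mL for Cmax.

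Protocol Section 5.6 says: "Exposure limits of AUC 0-24 of 15 ug.h/mL and C max of 1.5 ug/mL were set, based on information in Section 3.3". The Day 14 footnote to Table 1 repeats them, "AUC 0-24 = 15 ug.h/mL or C max = 1.5 ug/mL] on Day 14", and the heart pathology row of the Section 3.3.1 risk table gives the same pair.

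The SAP's figures match the superseded Table 1 reproduced under Amendment 2 in protocol Appendix 9: "exceeding the exposure limits [AUC 0-24 = 4.9 ug.h/mL or C max = 0.443 ug/mL] on Day 14". The Amendment 3 log gives the reason for the change, "New non-clinical data supports increasing the AUC & Cmax limits dictating dose level choices in the study", and describes the Section 5.6 revision as "Updated probability rates table based on increased AUC & Cmax exposure limits".

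SAP Section 1.1 states that the amended SAP rests on protocol Amendment 5, and that its first version rested on Amendment 2. The protocol chronology in SAP Section 1 records that Amendment 3 increased the exposure limits. SAP Section 2.1 declares one departure from the protocol, the bi-linear Bayesian model.

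**The concern.** The old values inside the protocol's amendment history are not an error. SAP Section 3.1 is different, because it is current text. The SAP's opening description puts support of the dose escalation analyses within its scope, and SAP Section 5.1 leaves Doses 4 and 5 open. The likeliest explanation is text carried over from the first SAP version, written when 4.9 and 0.443 were correct.

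Protocol Section 11 accepts a dose if the predicted probability of an individual exceeding the limits on any dosing day is no more than 10%. A modeller who took the limits from the SAP and the 10% from the protocol would be testing doses against thresholds about a third of the intended size. At stake is the wrongful rejection of a dose that the protocol allows.

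**Working it through.** **Inputs**

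| Source | AUC0-24 (ug.h/mL) | Cmax (ug/mL) |
|---|---|---|
| SAP 3.1 (current) | 4.9 | 0.443 |
| Protocol Appendix 9, Amendment 2 Table 1 (superseded) | 4.9 | 0.443 |
| Protocol 3.3.1, 5.6 and Table 1 (current) | 15 | 1.5 |

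**1. Reproduce the protocol's own margin.** The skin depigmentation row of Section 3.3.1 gives a dog exposure of 59.4 without the finding, and a 4-fold margin to the cap. 59.4 / 15 = 3.96, which agrees. With the old cap, 59.4 / 4.9 = 12.1, which matches the margin of more than 10-fold in the Amendment 2 text. The current protocol therefore works from 15.

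**2. Size of the discrepancy.** AUC: 15 / 4.9 = 3.06. Cmax: 1.5 / 0.443 = 3.39.

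**3. Direction.** Anyone above 15 is also above 4.9, and likewise for Cmax. At any dose, the lower limits can only raise the computed exceedance probability.

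**4. Tabulated Day 14 probabilities against the 10% rule**

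| Maintenance dose | Limits 4.9 / 0.443 (superseded Table 1) | Limits 15 / 1.5 (current Table 1) |
|---|---|---|
| 5 mg | <1% | <1% |
| 10 mg | 7.9% | <1% |
| 20 mg | not given | <1% |
| 30 mg | not given | 5.8% (6.9% on Day 1) |

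Under the SAP limits, 10 mg passes with 2.1 percentage points to spare. Under the protocol limits, 30 mg passes.

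**5. Cross-check, assuming exposure is proportional to dose.** 3 x 4.9 = 14.7, below 15, and 3 x 0.443 = 1.329, below 1.5. So 10 mg against the SAP pair is at least as likely to exceed as 30 mg against the protocol pair, that is, at least 5.8%. The superseded table's 7.9% is consistent with this.

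**6. 30 mg against the SAP limit.** Table 1 gives 100% at 10 mg for the "per trial probability of >90% of participants exceeding the target exposure for efficacy", with a target of 1.74 ug.h/mL. On proportionality, more than 90% of participants at 30 mg would exceed 3 x 1.74 = 5.22, hence also 4.9. That is far outside the 10% rule, yet SAP Section 5.1 lists 30 mg as Dose 3.

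**7. 20 mg against the SAP limit.** The documents give no figure. At 20 mg a participant exceeds 4.9 when his 10 mg exposure would exceed 4.9 / 2 = 2.45. To pass, at most 10% could lie above 2.45 while more than 90% lie above 1.74, so over 80% would have to fall between 1.74 and 2.45. Rejection is therefore likely. Putting a probability on it needs the between-participant variability, which the documents do not report.

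**The case against.** The strongest reply is that no decision depends on the SAP's numbers. The protocol's acceptance rule and the committee's power to raise the dose (Section 11), and the exposure stop (Section 8.2), all cite protocol Section 5.6. No display listed in SAP Appendix 10 reports an exceedance probability. The dose escalation deliverable there is an efficacy analysis, and the PK tables and figures belong to the final delivery. The population PK data file follows a separate Data Analysis Plan. Protocol Section 11 calls Cohort 3 the highest dose cohort and refers to later cohorts at a lower dose; at 10 mg or below, even the old limits would not block a dose.

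Nearly all of this stands, and it makes the effect minor. It does not make the text right. The SAP claims dose escalation support as part of its scope, states the limits explicitly, and gives no sign that they are historical.

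A reader might infer that earlier dose decisions were made against the wrong limits. The documents do not support that. The SAP lists 15 and 30 mg, and protocol Section 10.1.2 reports data at 15 mg; step 6 shows that 30 mg could not have passed under the old limits. A reader might also infer that 20 mg was about to be refused. The table of "Probability rates of individual participants for proposed loading and maintenance doses" includes it, but neither document says which dose was planned next.

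**Conclusion.** The concern holds as an inconsistency between protocol and SAP, minor in practical effect. The limits of 15 and 1.5 are not challenged as a design choice. The SAP figures are too low by 3.06-fold (AUC) and 3.39-fold (Cmax). The error cannot lead to overexposure, so reading it as a safety hazard would be wrong.

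If the SAP limits were applied with the 10% rule, the ceiling would fall from at least 30 mg, the top row of the current Table 1, to a little above 10 mg. The exposed case is a future dose between those values, and only if staff followed the SAP in place of protocol Section 5.6.

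The two ratios and the direction need no assumption. Steps 5 to 7 assume dose proportionality. Comparing Table 1 with the 10% rule takes its percentages as an individual's probability. Its footnotes call them per-trial probabilities of an individual participant exceeding; if they mean that any participant in a trial exceeds, individual probabilities are lower and the room above 10 mg is somewhat larger.

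**What to change.** In SAP Section 3.1, replace 4.9 and 0.443 with 15 ug.h/mL and 1.5 ug/mL, or remove the numbers and refer to protocol Section 5.6. The cross-reference is safer because it cannot go stale if the limits change again. Confirm on file that the dose escalation simulations used the current limits.

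The SAP reference list still cites the Amendment 2 protocol. Updating it is optional housekeeping, since SAP Section 1.1 already names Amendment 5 as the basis.

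The cost is one sentence of SAP text and a check of the simulation files. No protocol amendment and no new data are needed.
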